7.9.1 Adverse events / adverse drug reactions

Reporting of adverse events (AEs) in this study will focus on serious and non-serious adverse drug reactions (ADRs) to Pradaxa[®] and VKA, fatal AEs and pregnancies. All analyses of ADRs and fatal AEs will be based on the number of patients with ADRs and fatal AEs and NOT on the number of ADRs and fatal AEs.

For analysis multiple AE occurrence data in the eCRF will be collapsed into an AE provided that all of the following applies:

- All AE attributes are identical (lowest level term, intensity, action taken, therapy required, seriousness, reason for seriousness, relationship, outcome).
- The occurrences were time-overlapping or time-adjacent (time-adjacency of 2 occurrences is given if the second occurrence started on the same day or on the day after the end of the first occurrence).

For further details on summarization of AE data, please refer to [\(4, 6\)](#).

Occurrences of AEs will be analysed relative to the number of patients treated as well as observed person-years (i.e. time at risk). Analysis of AEs will be based on the concept of treatment emergent AEs. Patients will be analysed according to the anticoagulation treatment received at the onset of the AE. If no concurrent anticoagulation treatment is administered, then AEs occurring within a washout period of 3 days (for Pradaxa[®]) or 6 days (for VKA) after discontinuation of anticoagulation treatment will be assigned to the last treatment given. This washout period will also be included as time at risk for derivation of total person-years. AEs that deteriorate under treatment will also be considered as “treatment emergent”. Events occurring prior to first intake of anticoagulation treatment prescribed at baseline, during periods without any anticoagulation treatment (excluding washout periods), or after the end of the 6 month follow-up (excluding washout periods) will not be considered treatment emergent AEs and will not be included in the summary tables.

According to ICH E3 [\(7\)](#), AEs classified as ‘other significant’ needs to be reported and will include those non-serious AEs with

- (i) ‘action taken = discontinued’ or ‘action taken = reduced’, or
- (ii) marked haematological and other lab abnormalities or lead to significant concomitant therapy as identified by the Clinical Monitor/Investigator at a Medical Quality Review Meeting.

An overall summary of ADRs and fatal AEs will be presented. The frequency of patients with ADRs or fatal AEs will be summarised by treatment, primary system organ class and preferred term (mention MedDRA levels to be displayed in the tables). Separate tables will be provided to summarize ADRs or fatal AEs leading to discontinuation of anticoagulation treatment, serious ADRs or fatal AEs, ADRs leading to deaths and fatal AEs, and ADRs or

fatal AEs leading to dose change (including dose reduced, increased, and discontinued and re-introduced). Patient with pregnancies will be listed.

The primary system organ classes will be sorted in alphabetic order; preferred terms will be sorted by frequency (within system organ class).

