9.2.2.3 Visit schedule

Collection of patient data should be managed during routine practice visits. The time-schedule below can only be a recommendation; if a patient does not visit the site at these time points, data will not be collected (no visits will be conducted solely for study purposes).

Visits must be performed face-to-face and cannot be performed by phone, email or fax, as the patient has to complete the self-administered questionnaires.

1. At Baseline (at initiation on Pradaxa[®] or VKA)
2. 30-45 days after initiation on Pradaxa[®] or VKA (initiation period)

3. 150-210 days after initiation on Pradaxa® or VKA (continuation period)

Table 9.2.2.3: 1 Flow Chart / Schedule of Data Collection

Visit	1	2	3
Assessment	Baseline	Initiation period	Continuation period
Day	1	30-45 days	150 – 210 days
Informed Consent ¹	X		
Patient demographics: age, gender	X		
Concomitant diseases / co-morbidities	X	X	X
Concomitant therapies	X	X	X
Healthcare system characteristics ²	X		
HAS- BLED score (to be calculated in the eCRF)	X		
CHA ₂ DS ₂ -VASc score (to be calculated in the eCRF)	X		
Inclusion/exclusion criteria	X		
Duration of previous VKA treatment (for Cohort A)	X		
Reasons for switch to Pradaxa® (for Cohort A)	X		
Start Pradaxa® or VKA	X		
Pradaxa® dosing (110 or 150 mg) and reasons for dose changes	X	X	X
Creatinine clearance calculation ³	X	X	X
Weight ⁴	X	X ⁴	X ⁴
ADR (serious and non-serious), fatal AE, pregnancy collection		X	X
Reason for Pradaxa®/VKA discontinuation		X	X
PACT-Q1 questionnaire	X (for Cohort B only)		
PACT-Q2 questionnaire	X (for Cohort A only)	X (both Cohorts)	X (both Cohorts)

Footnotes:

1. Written Informed Consent must be obtained prior to the baseline visit assessments.
2. The type of hospital/practice and speciality of treating physician must be entered
3. Creatinine clearance can only be calculated in the eCRF (via Cockcroft-Gault Formula) if serum creatinine value is available from already existing laboratory reports. No lab assessment must be performed for the study at the baseline Visit 1, Visit 2 and/or Visit 3. See also footnote 4.
4. Weight must be determined at Visit 1. At Visit 2 and/or 3, only if existing serum creatinine value is available at Visit 2 and/or 3.

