9.7.5 Safety Analyses

Safety analyses will be performed separately for Cohort A and B, and will include all enrolled patients with an actual follow-up. Statistical analysis and reporting of AEs will be descriptive in nature, will be based on BI standards, and will focus on adverse drug reactions (ADRs) to Pradaxa[®] and VKA. No hypothesis testing is planned.

Occurrences of ADRs will be analyzed relative to the number of patients treated as well as observed person-years (i.e. time at risk). Safety analysis will be based on the concept of treatment emergent ADRs. Patients will be analyzed according to the anticoagulation treatment received at the time of the event. If no concurrent anticoagulation treatment is administered, then events occurring within a washout period of 3 days (for Pradaxa[®]) or 6 days (for VKA) after discontinuation of anticoagulation treatment will be assigned to the last treatment given. This washout period will also be included as time at risk for derivation of total person-years. ADRs that deteriorate under treatment will also be considered as “treatment emergent”. Events occurring prior to first intake of anticoagulation treatment prescribed at baseline, during periods without any anticoagulation treatment (excluding washout periods), or after the end of the 6 month follow-up (excluding washout periods) will not be considered treatment emergent events and will not be included in the summary tables.

The following parameters will be included in the safety analyses:

- Adverse drug reactions
- Adverse drug reactions leading to discontinuation of anticoagulation treatment
- Serious adverse drug reactions
- Adverse events leading to deaths

Schedule of Planned Analyses

No interim analysis is planned for Cohort A.

For Cohort B, it is planned that an interim analysis that assesses the comparability of patients in the Pradaxa[®] and VKA groups based on propensity scores will be performed when approximately half of the target sample size is reached (see details in Section 9.7.2.1).

For each cohort, the final analyses as specified in Section 9.7.2 will be performed once the data collection is completed, the data sets are cleaned, and the database is locked for that cohort. The final analysis for both cohorts may be performed together, if their complete data becomes available at the same time. One final report will be prepared at the completion of both cohorts.

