6.3 PATIENT SETS ANALYSED

The main analysis population will consist of all eligible patients [i.e. all patients who took the prescribed treatment and without an important protocol violation (see [Table 6.2: 1](#))] from all participating countries.

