7. PLANNED ANALYSIS

For End-Of-Text (EoT) tables, the set of summary statistics is: N / Mean / SD / Min / Median / Max.

Tabulations of frequencies for categorical data will include all possible categories and will display the number of observations in a category as well as the percentage (%) relative to the respective treatment group (unless otherwise specified, all patients in the respective patient set whether they have non-missing values or not). Percentages will be rounded to one decimal place. The category missing will be displayed only if there are actually missing values.

The summary of data will be done by cohort and by treatment (Pradaxa[®] or VKA) within Cohort B.

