7.9 SAFETY ANALYSIS

Safety analyses will be performed separately for Cohort A and B and by treatment for Cohort B, and will include all eligible patients. Statistical analysis and reporting of safety parameters will be descriptive in nature; and will be based on BI standards. No hypothesis testing is planned.

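### The SAP drops the protocol's follow-up condition from the safety set, so treated patients with no post-baseline contact dilute the crude ADR percentages by up to their share of the denominator

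*SAP*

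**What the plan says.** The protocol and SAP name different safety populations.

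- Protocol 9.7.5: safety analyses "will include all enrolled patients with an actual follow-up". The term is not defined.
- SAP 7.9: safety analyses "will include all eligible patients". SAP 6.3 defines these as "all patients who took the prescribed treatment and without an important protocol violation". No follow-up is required.
- SAP 10 (history table) lists the change of safety set among the January 2018 revisions and gives no reason. SAP 4.1 mentions only the updated patient analysis set.

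The sentence on denominators is almost the same in both. SAP 7.9.1 has "Occurrences of AEs will be analysed relative to the number of patients treated as well as observed person-years (i.e. time at risk" and Protocol 9.7.5 has "Occurrences of ADRs will be analyzed relative to the number of patients treated as well as observed person-years (i.e. time at risk". What changed is the set to which it applies. SAP 7 adds that, unless otherwise specified, percentages are taken over "all patients in the respective patient set whether they have non-missing values or not".

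On ascertainment, the flow chart in Protocol 9.2.2.3 marks ADR, fatal AE and pregnancy collection at Visits 2 and 3 only. Visits must be face to face, and the same section says: "if a patient does not visit the site at these time points, data will not be collected (no visits will be conducted solely for study". Protocol 11.2, however, requires ADRs, fatal AEs and pregnancies to be entered from consent to the end of the study, and sets 24-hour and 7-day reporting limits for patients on Pradaxa. Neither requirement is tied to a visit.

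**The concern.** A table of patients with an ADR has two outcomes: recorded or not recorded. A patient who took a first dose and was not heard from again falls in the second group and reads as ADR-free, although nobody asked. The missing-value category that SAP 7 provides for other tables does not reveal this, because absence of an event record is not a missing value.

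The protocol's follow-up condition kept such patients out of the denominator. Without it, the crude ADR percentages by cohort, and by drug within Cohort B, mix observed and unobserved patients. If the unobserved share differs between Pradaxa and VKA, part of any difference between the two percentages reflects ascertainment, and the table gives no means of telling how much. The issue would remain even if no patient had an important protocol violation.

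**Working it through.** **Inputs.** The documents state neither an ADR rate nor a share of patients without post-baseline contact, so there is no planned figure to reproduce. The only loss figures are in Protocol 9.5: 20% loss to follow-up of 598 patients in Cohort A (598 × 0.80 = 478 remaining), and 30% for loss and matching combined of 1192 in Cohort B. Neither is the quantity needed. Both include loss after Visit 2, and the second also includes matching loss. I use 20% only as the upper end of an assumed range.

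**Formula.** Let p be the true ADR risk, assumed equal in patients who return and those who do not; f the share of treated patients with no post-baseline contact; and c the fraction of those patients' ADRs that still reach the eCRF.

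Reported percentage = p × [(1 − f) + f × c]; relative shortfall = f × (1 − c), which is at most f.

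**Results for an illustrative p = 10%:**

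| f (assumed) | c = 0 | c = 0.5 |
|---|---|---|
| 5% | 10 × 0.95 = 9.5% | 10 × (0.95 + 0.025) = 9.75% |
| 10% | 10 × 0.90 = 9.0% | 10 × (0.90 + 0.05) = 9.5% |
| 20% | 10 × 0.80 = 8.0% | 10 × (0.80 + 0.10) = 9.0% |

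The c = 0 column is the worst case. In head counts, if the whole 20% loss in Cohort A fell before Visit 2 and nothing else was captured, 48 patients with an ADR would give 48/598 = 8.0% instead of 48/478 = 10.0%.

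**How the denominator is repaired matters.** Take 100 treated patients, of whom 20 do not return, with p = 10% and c = 0.5. The 80 who return contribute 8 patients with an ADR. The 20 who do not return have 2, of which 1 is recorded.

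- All treated, as in the SAP: (8 + 1)/100 = 9.0%.
- Followed-up patients, defined by ascertainment: 8/80 = 10.0%.
- Followed-up patients plus any non-returner with a reported event: (8 + 1)/(80 + 1) = 11.1%.

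The third option lets the outcome decide who enters the denominator, and its error is about as large as the SAP's in the opposite direction.

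**The case against.** The case for leaving the SAP alone has real substance.

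- **Recording outside visits.** A reader might infer that no ADR can be recorded in a patient who does not return. Protocol 11.2 does not support that, since collection runs from consent onwards. This stands, and it makes f an upper limit on the shortfall. It does not remove the problem: a collection period schedules no contact with someone who stays away.
- **Person-year rates and follow-up summaries.** SAP 7.9.1 also gives rates per person-year, and SAP 6.6 summarises discontinuation from treatment and follow-up by treatment. Both help. The rates do not correct the percentages, however, and SAP 7.8 needs a date of last administration without a rule for a living patient who does not return. The SAP 6.6 summary does not single out patients lost before Visit 2.
- **Late attenders.** SAP 6.1 accepts Visit 2 data from days 7 to 124 and Visit 3 data from days 125 to 365, so a late visit is not a lost one. This stands and makes a large f less likely.
- **Direction between drugs.** A reader might infer that the less-seen drug will look safer, because Protocol 9.9 expects VKA patients to be seen more often. That remark concerns observer bias and visit frequency, not the share never returning. The expedited form in Protocol 11.2 applies to Pradaxa patients only, which could push ascertainment the other way. The sign is unknown.
- **Importance.** Safety is descriptive, no test is planned, and the primary objective is PACT-Q perception. This stands and limits the weight of the point.

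**Conclusion.** The point holds as a limited one. SAP 7.9 with 6.3 removes a protocol condition without explanation, and the crude ADR percentages are then diluted by at most the share of treated patients with no post-baseline contact: at most 5%, 10% or 20% in relative terms if that share is 5%, 10% or 20%. These shares are assumptions.

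The bound also assumes equal risk in returners and non-returners. If patients stay away because of a reaction, the shortfall could be larger, and a followed-up denominator would not recover it. That is a further reason to show the unfollowed count.

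Two stronger readings are not supported. It cannot be said that the reported percentages will be too low by a known amount, or that they will be lower than the protocol's set would have given: the SAP set also removes patients with important protocol violations and requires drug intake, so the net change cannot be signed. Nor can the 20% and 30% planning allowances be read as the size of the dilution. No PACT-Q result is affected.

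**What to change.** In SAP 7.9 and 7.9.1:

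1. Base the ADR percentages on treated patients with an actual follow-up, defined as a post-baseline visit or contact at which ADRs were ascertained. Having had an event must not by itself qualify a patient.
2. Show the percentage over all treated patients beside it, so that early deaths and ADRs reported without a visit remain visible.
3. Give the number treated without post-baseline contact, by cohort and by drug within Cohort B.
4. For patients who do not return, end person-time at the last contact, and add this rule to SAP 7.8.
5. State in SAP 4.1 why the safety set differs from the protocol's.

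The cost is one flag in the analysis data set, a few sentences, one line for the count and one extra column in the safety tables. Denominators become slightly smaller and percentages slightly higher. No new data are needed.

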11.2 ADVERSE EVENT AND SERIOUS ADVERSE EVENT COLLECTION AND REPORTING

The investigator shall maintain and keep detailed records of all AEs in their patient files.

Collection of AEs

The study design is of non-interventional nature and the study is conducted within the conditions of the approved marketing authorisation. Sufficient data from controlled interventional trials are available to support the evidence on the safety and efficacy of the studied BI drug. For this reason the following AE collection and reporting requirements have been defined.

The following must be collected by the investigator in the (e)CRF from signing the informed consent onwards until the end of the study:

- all adverse drug reaction (ADRs) (serious and non-serious),
- all AEs with fatal outcome,
- all pregnancies

Note: For all patients on Pradaxa[®] these data must be recorded on the AE pages in the eCRF. The separate NIS AE form or Pregnancy Monitoring Form must be used for Pradaxa[®] patient only (see 'Expedited Reporting' below).

All ADRs, including those persisting after study completion must be followed up until they are resolved, have been sufficiently characterized, or no further information can be obtained.

The investigator carefully assesses whether an AE constitutes an ADR using the information below.

Causal relationship of adverse event

The definition of an adverse reaction implies at least a reasonable possibility of a causal relationship between a suspected medicinal product and an adverse event. An adverse reaction, in contrast to an adverse event, is characterised by the fact that a causal relationship between a medicinal product and an occurrence is suspected.

Medical judgment should be used to determine the relationship, considering all relevant factors, including pattern of reaction, temporal relationship, de-challenge or re-challenge, confounding factors such as concomitant medication, concomitant diseases and relevant history.

Arguments that may suggest a **reasonable causal relationship** could be:

- The event is **consistent with the known pharmacology** of the drug
- The event is known to be caused by or **attributed to the drug class**.
- A **plausible time to onset of the event** relative to the time of drug exposure.
- Evidence that the **event is reproducible** when the drug is re-introduced
- **No medically sound alternative etiologies** that could explain the event (e.g. preexisting or concomitant diseases, or co-medications).

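### Fatal AEs are collected to the end of the study, but those starting in untreated time beyond a 3-day (Pradaxa) or 6-day (VKA) washout enter no AE summary table, so the planned tables do not give the all-cause death count

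*SAP*

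**What the plan says.** **Collection.** Protocol 11.2 requires the investigator to record three things: ADRs, pregnancies and "all AEs with fatal outcome". Fatal AEs are listed separately from ADRs, so no causal link is needed. The period runs "from signing the informed consent onwards until the end of the study" and is not tied to being on drug.

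**Tabulation.** SAP 7.9.1 bases the AE analysis on treatment-emergent events and assigns them by onset: "Patients will be analysed according to the anticoagulation treatment received at the onset of the AE". A patient who has stopped is covered by this condition: "If no concurrent anticoagulation treatment is administered", the event still goes to the last drug provided that it occurs "within a washout period of 3 days (for Pradaxa[®]) or 6 days (for VKA) after discontinuation of anticoagulation treatment". Events that begin "during periods without any anticoagulation treatment (excluding washout periods") "will not be considered treatment emergent AEs and will not be included in the summary tables". The same sentence also removes events before first intake and after the six-month follow-up. Protocol 9.7.5 has the same windows and exclusions, so the two documents agree.

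**Displays.** SAP 7.9.1 plans frequency tables for ADRs and fatal AEs, including one for deaths. The only listing it names is for another purpose: "Patient with pregnancies will be listed".

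**The concern.** A treatment-emergent filter suits ADR tables, where the question is what happened on drug. It suits all-cause deaths less well. The protocol chose to collect fatal AEs without a causality condition and without an on-treatment condition, and SAP 7.9.1 names fatal AEs as a focus of reporting. The filter then applies to them with no exception.

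A reader of the report will normally take a table of fatal AEs to show how many patients died. Here it would show only deaths whose AE began on an anticoagulant or within a few days of stopping. The filter also drops a late-onset event that the investigator has judged to be an ADR. Protocol 11.2 already tells investigators that an implausible time to onset argues against causality, so such an event has passed that test before the table removes it.

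The windows also differ by drug, which raises a secondary question about comparing the Pradaxa and VKA columns in Cohort B.

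**Working it through.** The plan states no figure to reproduce. The check is a comparison of rules, followed by an illustration.

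**Step 1: follow one event through the rules.** Take a fatal AE starting on day 5 after the last dose, within the six-month follow-up, with no replacement anticoagulant.
- Collected? Yes on either drug, under protocol 11.2.
- In the SAP 7.9.1 tables after VKA? Yes, since 5 ≤ 6.
- In the SAP 7.9.1 tables after Pradaxa? No, since 5 > 3.
- From day 7 onwards the event is outside the tables on both drugs.

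**Step 2: vary onset and treatment status.**
- AE starts on drug, patient stops, death follows weeks later: counted, because onset decides.
- AE starts within the washout: counted.
- AE starts after a switch to another anticoagulant: analysed under the treatment received at onset.
- AE starts in untreated time after the washout: not in the summary tables.

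**Step 3: how much off-drug time the tables leave out.** Inputs: washout w = 3 days (Pradaxa) or 6 days (VKA), from SAP 7.9.1. Follow-up F = 180 days is an assumed value for six months; F = 210 is the upper end of the protocol's Visit 3 window. The stop day s is assumed, with no replacement and no restart.

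Off-drug days = F − s. Days outside the tables = F − s − w.

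| F | s | Off-drug days | Outside, Pradaxa | Outside, VKA |
|---|---|---|---|---|
| 180 | 30 | 150 | 147 (98%) | 144 (96%) |
| 180 | 90 | 90 | 87 (97%) | 84 (93%) |
| 180 | 150 | 30 | 27 (90%) | 24 (80%) |
| 210 | 15 | 195 | 192 (98%) | 189 (97%) |
| 210 | 150 | 60 | 57 (95%) | 54 (90%) |

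**Step 4: the unequal windows.** The difference is 6 − 3 = 3 days per patient who stops, or 3/90 = 3.3 percentage points of off-drug time in the 180/90 row. SAP 7.9.1 adds the same washout to time at risk, so numerator and denominator match in the person-year rates. Counts and percentages per patient treated have no such match. Most of the loss comes from the exclusion itself.

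**The case against.** The strongest case against has five parts.

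- **The rule is prespecified, consistent and descriptive.** Protocol 9.7.5 and SAP 7.9.1 agree, safety is not a study objective, and no hypothesis is tested. This stands and limits the weight of the point, but it does not make an on-treatment filter suitable for all-cause deaths.
- **Deaths after discontinuation do not all disappear.** A reader might infer that they do, including a death from an ADR that led to stopping. The documents do not support that: attribution follows onset, and SAP 7.9.1 plans tables for events leading to discontinuation and for ADRs leading to death. Only fatal AEs with onset beyond the washout are lost.
- **The deaths may surface elsewhere.** SAP 6.6 summarises reasons for leaving treatment and follow-up. Fatal AEs in Pradaxa-exposed patients reach the sponsor within 24 hours (protocol 11.2). The sponsor's AE standards, cited in the SAP but not available here, may require a death listing. So it is not established that the report could not state how many patients died. However, the disposition summary promises no cause, last drug or time since last dose, and the expedited form does not cover VKA patients.
- **Naming one listing does not rule out others.** This is fair: the SAP has no catalogue of listings. The gap is that no display of these deaths is stated.
- **The affected group may be small.** A patient must stop, take no replacement, and then have a new fatal AE after the washout. The documents give no figure for this.

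**Conclusion.** The point holds as a reporting gap. Followed as written, the AE summary tables do not give the all-cause death count that protocol 11.2 collects, because fatal AEs with onset in untreated time beyond 3 days (Pradaxa) or 6 days (VKA) are left out. This rests on the text alone.

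Its size in deaths is unknown. With an assumed 180-day follow-up and a stop on days 30 to 150, the tables leave out 90% to 98% of off-drug time on Pradaxa and 80% to 96% on VKA. A reader might take these as shares of deaths; they are not.

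Two other inferences should be resisted. One is that the shorter washout makes the Pradaxa column look materially better. The difference is 3 days per patient who stops, it bears mainly on per-patient counts, and its direction in practice depends on how many patients stop in each group and for how long. The other is that thromboembolic deaths are to be expected after stopping; the documents give no source for that.

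**What to change.** Keep the treatment-emergent tables. Add to SAP 7.9.1:

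- one summary and one listing of all fatal AEs collected from consent to end of study, by cohort and initial treatment, regardless of treatment status at onset;
- in the listing, the last anticoagulant taken, days since last dose and the investigator's causality assessment;
- in the same listing, a flag for ADRs excluded from the tables only because onset fell outside the washout.

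Starting at consent matches the collection period and picks up any death before first intake. Such a patient took no prescribed treatment and is outside the eligible set in SAP 6.3, so the display should cover all consented patients. If the sponsor's AE standards already require a death listing, a sentence in the SAP saying so and fixing its scope would settle that part.

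The cost is SAP wording, one table and one listing from data already collected. Reported death counts may be slightly higher than in the treatment-emergent tables, and a short note should explain the difference.

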11. MANAGEMENT AND REPORTING OF ADVERSE EVENTS/ADVERSE REACTIONS

11.1 DEFINITIONS OF ADVERSE EVENTS

Adverse event

An adverse event (AE) is defined as any untoward medical occurrence in a patient or clinical investigation subject administered a medicinal product and which does not necessarily have a causal relationship with this treatment. An adverse event can therefore be any unfavourable and unintended sign (e.g. an abnormal laboratory finding), symptom, or disease temporally associated with the use of a medicinal product, whether or not considered related to the medicinal product.

Adverse reaction

An adverse reaction is defined as a response to a medicinal product which is noxious and unintended. Response in this context means that a causal relationship between a medicinal product and an adverse event is at least a reasonable possibility. Adverse reactions may arise from use of the product within or outside the terms of the marketing authorisation or from occupational exposure. Conditions of use outside the marketing authorization include off-label use, overdose, misuse, abuse and medication errors.

Serious adverse event

A serious adverse event is defined as any AE which

- results in death,
- is life-threatening,
- requires in-patient hospitalization, or
- prolongation of existing hospitalisation,
- results in persistent or significant disability or incapacity, or
- is a congenital anomaly/birth defect

Life-threatening in this context refers to a reaction in which the patient was at risk of death at the time of the reaction; it does not refer to a reaction that hypothetically might have caused death if more severe.

Medical and scientific judgement should be exercised in deciding whether other situations should be considered serious reactions, such as important medical events that might not be immediately life threatening or result in death or hospitalisation but might jeopardise the patient or might require intervention to prevent one of the other outcomes listed above. Examples of such events are intensive treatment in an emergency room or at home for allergic bronchospasm, blood dyscrasias or convulsions that do not result in hospitalisation or development of dependency or abuse. Any suspected transmission via a medicinal product of an infectious agent is also considered a serious adverse reaction.

Adverse Event of Special Interest (AESI)

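### SAP 7.9.1 joins fatal AEs of any cause to the protocol's three ADR parameters, names no ADR-only table, and does not declare the change

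*SAP*

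**What the plan says.** Protocol 9.7.5 states that the safety analysis "will focus on adverse drug reactions (ADRs) to Pradaxa[®] and VKA" and names four parameters. Three carry a causality requirement: ADRs, "Adverse drug reactions leading to discontinuation of anticoagulation treatment" and "Serious adverse drug reactions". The fourth, "Adverse events leading to deaths", does not.

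Protocol 11.1 makes an event an adverse reaction only where "a causal relationship between a medicinal product and an adverse event is at least a reasonable possibility". Protocol 11.2 sets what is collected: all ADRs, "all AEs with fatal outcome", and pregnancies. A non-fatal event therefore has to be collected only if it is judged related, and a fatal event whatever its cause.

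SAP 7.9.1 counts patients, not events. Its main table is described as "The frequency of patients with ADRs or fatal AEs will be summarised by treatment, primary system organ class and preferred term". It continues: "Separate tables will be provided to summarize ADRs or fatal AEs leading to discontinuation of anticoagulation treatment, serious ADRs or fatal AEs". The dose-change table is worded in the same joined way, and deaths also have a table of their own. No table limited to ADRs is named. SAP 4.1 lists two changes from the protocol, to the analysis set and to the Cohort B interim analysis. The history table records a revision to section 7.9, but only that safety analyses will include all eligible patients.

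**The concern.** The protocol asks how many patients had a drug reaction, a serious drug reaction, or a drug reaction that ended treatment. A count of patients with a related event or a death from any cause answers none of these. Nor is it an all-cause serious-event frequency, because unrelated non-fatal serious events are not required to be collected.

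The serious table is the most exposed. Under Protocol 11.1 an event that results in death is serious, so every treatment-emergent unrelated death falls into it, and serious reactions may be few. In Cohort B the protocol recognises possible channelling, and no propensity adjustment is planned for safety. A difference in background mortality between the Pradaxa and VKA groups could then move the combined frequency with no difference in drug reactions.

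**Working it through.** The documents state no ADR, serious-ADR or death frequency, so there is no planned figure to reproduce. The check has two parts.

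**1. The two plans side by side**

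- Any reaction. Protocol 9.7.5: ADRs. SAP 7.9.1: ADRs or fatal AEs.
- Discontinuation. Protocol: ADRs with that consequence. SAP: ADRs or fatal AEs with that consequence.
- Seriousness. Protocol: serious ADRs. SAP: serious ADRs or fatal AEs.
- Deaths. Protocol: adverse events leading to death. SAP: a separate table of ADRs leading to death and fatal AEs.
- Dose change. Not a protocol parameter. SAP: ADRs or fatal AEs with that consequence.

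The first three protocol parameters each gain a group that the protocol keeps in its fourth.

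A fatal AE judged unrelated enters as follows. It must be treatment-emergent, meaning on treatment or within the washout of 3 days (Pradaxa) or 6 days (VKA). If so, it enters the overall and serious tables. It enters the discontinuation or dose-change table only if recorded with that action.

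**2. Illustration of size**

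Inputs:

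- Group size 596, from the planned Cohort B total in Protocol 9.5: 1192 / 2 = 596. This is planned enrolment; the eligible set may be smaller.
- *a*, the true proportion of patients with the ADR type in question: assumed 1% (serious) or 10% (any).
- *d*, the proportion with a treatment-emergent unrelated fatal AE: assumed 0.5%, 1% or 2%.

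If the two are independent, the combined proportion is *a* + *d*(1 − *a*).

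Serious ADRs at 1% (596 × 0.01 = 6.0 patients):

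- *d* = 0.5%: 0.01 + 0.005 × 0.99 = 1.50%, or 8.9 patients
- *d* = 1%: 0.01 + 0.01 × 0.99 = 1.99%, or 11.9 patients
- *d* = 2%: 0.01 + 0.02 × 0.99 = 2.98%, or 17.8 patients

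The ratio to the true value runs from 1.50 to 2.98.

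Any ADR at 10% (59.6 patients):

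- *d* = 0.5%: 0.10 + 0.005 × 0.90 = 10.45%, or 62.3 patients
- *d* = 1%: 0.10 + 0.01 × 0.90 = 10.90%, or 65.0 patients
- *d* = 2%: 0.10 + 0.02 × 0.90 = 11.80%, or 70.3 patients

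The ratio runs from about 1.04 to 1.18.

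With no overlap at all the combined value is *a* + *d*: 1.5%, 2.0% and 3.0% in the first case, and 10.5%, 11.0% and 12.0% in the second. The independence assumption therefore matters little. Tables restricted to related events would return 1% and 10%.

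**The case against.** The strongest reply is that the SAP does what it says. It labels the tables as ADRs or fatal AEs and never calls them ADR rates. Its reporting scope matches what Protocol 11.2 collects, deaths have their own table, and relationship is recorded for each event. *Or* might mean separate rows. SAP 7.9 also relies on company standards that are not in the documents and might call for an ADR-only display. In a table by preferred term, an unrelated death appears under its own term, so it affects totals more than individual reaction terms.

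Much of this stands, and it rules out three stronger readings that a reader might infer.

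- *That ADRs are the protocol's only safety endpoint, so reporting fatal AEs departs from it.* Deaths are a listed parameter and all fatal AEs are collected. Only the joining departs from the protocol.
- *That the SAP reports a false ADR rate.* The tables are labelled as composites. The ADR frequency is omitted from the named tables rather than misstated.
- *That every unrelated death inflates every table.* Only treatment-emergent deaths count, and the action-based tables need the action to be recorded.

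The channelling argument is also limited. The protocol says channelling can occur, not that it will. Sicker patients may have more true reactions too, so ADR-only tables would not remove that imbalance.

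The reply does not restore the missing parameters. A frequency of patients with one thing or another ordinarily means a union, and nothing in the documents requires an ADR-only count. That the split can be recovered from the data does not mean it is planned.

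**Conclusion.** The concern holds as a mismatch between protocol and SAP, of minor severity. Followed as written, SAP 7.9.1 replaces three protocol safety parameters with composites of related events and deaths of any cause, and SAP 4.1 does not declare it.

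The likely effect is small for a common ADR frequency and potentially large in relative terms for a rare serious-ADR frequency: a factor of about 1.5 to 3 at an assumed 1%. Every event rate behind those figures is an assumption. They show where the composite matters, not what this study will find. The conclusion also rests on reading *or* as a union.

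Safety is descriptive with no hypothesis testing, and no PACT-Q2 result is touched, which keeps the severity low.

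**What to change.** In SAP 7.9.1, restrict the ADR, serious-ADR, ADR-discontinuation and ADR-dose-change tables to events judged related. A fatal event then enters them only if it was judged an ADR and meets that table's condition. Show all fatal AEs in the existing death table, split by relationship.

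If the combined tables are kept, label them as supplementary composites and list the change in SAP 4.1. If separate rows were intended all along, one sentence saying so settles it.

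The cost is a few sentences, one filter on a variable already recorded, and a few extra tables if both versions are shown. No new data are needed.
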